8.1.2 Multivariate display of immunogenicity endpoints

Data visualization techniques may be used to explore the relationship among immunogenicity readouts. The set of readouts may be based on one of the primary endpoints (eg, ICS), on the set of primary endpoints, or on immunogenicity endpoints that also include secondary or exploratory endpoints. To understand the relationship between pairs of readouts, scatter plots may be used when the number of readouts is small or for a larger number of readouts, a heatmap showing the degree of correlation between any two pairs. Principal component analysis (PCA) and associated ‘biplots’ of the scores and loadings are particularly useful to understand associations between readouts, especially when readouts are correlated [3]. PCA is a method to reduce the dimensionality of the number of readouts to a smaller set of values (principal components) that are normalized linear combinations of the readouts in such a way that the first principal component accounts for the most variability in the data and subsequent components, while maximizing variability, are uncorrelated with each other. A ‘biplot’ displays the first and second principal component scores and principal component loadings. The x-axis is the value from the first principal component and the y-axis is the second principal component, where each axis label includes the percentage of variation in the total set of readouts captured by the principal component. The top axis is the first principal component loadings and the right axis is the second principal component loadings. An arrow is drawn for each immunogenicity readout (eg, Env-specific CD4+ T-cell polyfunctionality score, Env-specific CD8+ T-cell total magnitude) from the origin to the point defined by its first two principal component loadings. The length of the arrow represents the amount of total variation of the set of readouts captured by the given readout. The direction of an arrow conveys the extent to which the variation of a readout is in the direction of the first or second principal component. The angle between two arrows conveys information about the correlation of the two readouts, with a zero-degree angle denoting perfect correlation and a 90-degree angle denoting no correlation. Each arrow on the biplot is labeled by the immunogenicity readout it represents. A biplot is annotated with key meta-information such as the treatment arm (most common application) or a demographic category. Depending on the application, K-means clustering and hierarchical clustering may also be applied for multivariate graphical display of immunogenicity readouts.

8.1.3 Primary analyses of neutralization magnitude-breadth curves

The area-under-the-magnitude-breadth curve (AUC-MB) to a global panel of viral isolates [4] will be computed for each participant with evaluable neutralization data, as described in [5]. AUC-MB to a vaccine-matched panel may also be computed when the panel consists of at least 3 isolates. Tier 1A viral isolates will not be included in AUC-MB analyses. Dunnett’s procedure will be applied with 2-sided alpha = 0.05 to determine which of the [n] vaccine groups have a significantly higher mean AUC-MB than that of the pooled placebo groups, as described in [2] (see their formula (1.1)). This procedure will be applied to construct 95% Cis about the [n] differences in mean AUC-MB for each vaccine regimen versus the pooled placebo

groups (vaccine – placebo), which simultaneously have at least 95% coverage probability.

8.1.4 Analysis of CD4+ and CD8+ T-cell responses as measured by the ICS assay

The analysis of CD4+ and CD8+ T-cell response rates as measured by the ICS assay will be evaluated and compared as described under the general approach. For each T-cell subset, the positivity call for each peptide pool will include a multiple comparison adjustment for the number of peptide pools used in the assay. In general, the Mixture Models for Single-cell Assays (MIMOSA) statistical framework [6] and/or the Fisher's exact test-based positivity criteria will be used. Details of the positivity criteria will be discussed in Section 9. The magnitude of marginal response will be analyzed as described for quantitative data in the general approach section. For each T-cell subset, graphs will be used to display the background-subtracted magnitudes for each participant by protein, treatment arm and timepoint. When 3 or more cytokines are being measured by the ICS assay, the polyfunctionality of ICS responses may also be analyzed as an exploratory endpoint. Besides descriptive plots of the magnitude of polyfunctional responses, the COMPASS (Combinatorial Polyfunctionality analysis of Antigen-Specific T-cell Subsets) statistical framework [7] may also be used to perform joint modelling of multiple T-cell subsets of different cytokine combinations. For example, the functionality score (FS) and the polyfunctionality score (PFS) may be used to summarize the multi-parameter ICS responses.

8.1.5 Analysis of multiplexed immunoassay data

When a small panel of analytes (eg, ≤ 5) is being assessed in a multiplexed immunoassay, the analysis of response rates and response magnitudes will be evaluated and compared as described under the general approach. Details for calculating a positive response and response magnitude will be provided in Section 9. When a larger panel is being assessed, two approaches may be considered to evaluate the magnitude and breadth of these responses. First, Magnitude–Breadth (M-B) curves maybe employed to display individual- and group-level response breadth as a function of magnitude. Response breadth is defined as the number of antigens, peptides, and/or isolates with associated magnitudes above the assay-specific positivity threshold. Two choices are to compare the M-B curves among vaccine arms, as follows: a non-parametric Wilcoxon rank sum test on the subject-specific AUC-MB or a Kolmogorov-Smirnov type test on the 2 group-average M-B curves. Simulations can be used to obtain 2-sided p-values for the latter test. Second, a weighted-average score-like variable may be constructed to account for the correlations between analytes as an integrate magnitude of responses to multiple analytes. Similar group comparison methods described in the first approach may be adopted. Details of either approach will be described in Section 9.

9 IMMUNOGENICITY TABLES AND FIGURES, BY ASSAY

9.1 Adenovirus Neutralizing Antibody

Similar to other neutralizing antibody assays, the Adenovirus Nab assay relies on incubation of participant samples with the virus(es) of interest, followed by incubation of the virus-sample mixture with infectable host cells expressing a reported gene.

Viral particles of GFP-expressing AdC6 or AdC7 are mixed with twofold serial dilutions (ranging from 1:10 to 1:10,240) of heat-inactivated sera and incubated. After incubation, HEK 293 cells are added per well. Following a 24-hour incubation, cells are fixed with paraformaldehyde and nuclei staining is performed with Hoechst 5 μ g/mL. Plates are analyzed under an epifluorescence microscope (BX41, Olympus) in 40 \times objective lens and approximate percentages of eGFP+ cells are noted for each well. Reported Nab titers correspond to the reciprocal dilutions in which the ratio of GFP-expressing/Hoechst-stained cells reached approximately 50% of the ratio observed in negative controls.

A calibration standard, consisting of mouse serum, is included on every plate and diluted in the same series as participant samples. This standard curve is assessed on each plate for Part A and per day for Part B by the lab and used to adjust titers of samples as needed. Positive controls consist of sera from BALB/c mice primed and boosted with viral particles of GFP-expressing vectors. Negative (virus mixture added with DMEM rather than sera) controls are also included on each plate and assessed internally for precision and consistency with previous validation results. Results are reported by the lab as percent in EGFP+ cells. Study samples as well as controls and standards are run in duplicate. SCHARP will calculate the ID50 titer, using all reported dilutions (10, 20, 40, 80, 160, 320, 640, 1280) and fitting a two-parameter log-logistic (LL.2) model for each participant, visit and isolate (pooling replicates). If all values in titration curves are less than 50% EGFP, ID50 will be censored at >1280 and will be set as 1280 in descriptive analysis. Non-responder will be defined as ID50 titer less than 10, and positive response be ID50 greater or equal to 10. For negative responders, half lowest dilution ($= 10/2 = 5$) will be assigned as the titer (ID50) and will be used in summary statistics.

For Part A of the study, neutralization titers will be measured on samples from week 0 (visit 2 – baseline) and week 4 (visit 4 – 4 weeks post vaccination). For Part B of the study, neutralization titers will be measured on samples from week 0 (visit 2 – baseline), week 4 (visit 4 – 4 weeks post 1st vaccination), week 16 (visit 7 – 4 weeks post 2nd vaccination).

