9.1.1 List of Tables

- Response rate table by lab, virus, visit number (visit month), and treatment arm (as applicable)
- Summary statistics for Ad Nab titers (min, 25th percentile, median, 75th percentile, max, mean, standard deviation) among all participants by lab, virus, visit number (visit month), and treatment arm (as applicable)
- Summary statistics for Ad Nab titers (min, 25th percentile, median, 75th percentile, max, mean, standard deviation) among participants with positive response by lab, virus, visit number (visit month), and treatment arm (as applicable)

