9.1.2 List of Graphs

- Boxplots of Ad Nab antibody titers by virus, visit number (visit month), and treatment arm.

- Spaghetti plots of Ad Nab titers by virus, and treatment arm over time.
- (If applicable) Boxplots of Ad Nab titers by virus, visit month (Month 0 and Month 1), and treatment arm with Part A and Part B side-by-side.

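### SAP 9.1 defines the AdC6/AdC7 titer relative to negative controls but censors on an unscaled 50% EGFP, and dilutes to 1:10,240 but fits and caps at 1280; both rules need reconciling (minor)

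*SAP*

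**What the plan says.** All the rules are in SAP section 9.1.

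- **Titer definition.** The reported titer is the reciprocal dilution at which the ratio of GFP-expressing to Hoechst-stained cells "reached approximately 50% of the ratio observed in negative controls". This is a relative 50%.
- **Data sent for analysis.** "Results are reported by the lab as percent in EGFP+ cells".
- **Model.** The statistical center calculates the ID50 by "fitting a two-parameter log-logistic (LL.2) model for each participant, visit and isolate (pooling replicates").
- **Upper censoring.** "If all values in titration curves are less than 50% EGFP, ID50 will be censored at >1280 and will be set as 1280". The threshold does not mention controls.
- **Dilution series in the assay.** The virus is mixed with "twofold serial dilutions (ranging from 1:10 to 1:10,240) of heat-inactivated sera".
- **Dilution series in the fit.** The ID50 is calculated "using all reported dilutions (10, 20, 40, 80, 160, 320, 640, 1280").
- **Controls.** Negative controls (virus with medium in place of serum) are on every plate. Their stated use is an internal check of precision and consistency. A mouse-serum standard may be used to adjust titers; it is assessed per plate in Part A and per day in Part B.
- **Low end.** An ID50 below 10 is a non-response and is entered as 5.

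The outputs are response rates and "Summary statistics for Ad Nab titers (min, 25th percentile, median, 75th percentile, max, mean, standard deviation) among all participants" (SAP 9.1.1), with a possible set of "Boxplots of Ad Nab titers by virus, visit month (Month 0 and Month 1), and treatment arm with Part A and Part B side-by-side" (SAP 9.1.2). The readout serves exploratory objective 5 (SAP 3.3), which concerns magnitude before and after vaccination. Letter of Amendment 2, Item 1, says the results are for research only and may help identify pre-existing immunity that interferes with other immunology assessments.

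**The concern.** Two rules that determine the ID50 do not agree with the text around them.

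**Scale.** A two-parameter log-logistic curve has its limits fixed at 0 and 100%, so only the midpoint and slope are estimated and the midpoint is an absolute 50%. The definition asks for 50% of the control. The two agree only if the control is 100% infected, or if each well is first divided by the control. The SAP states neither. Without that division, analysts who follow the text obtain a different quantity, and some sera with titers inside the range would meet the censoring rule and be raised to 1280.

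**Range.** The assay sentence and the fit sentence give series that end eight-fold apart. If wells beyond 1280 were read, higher titers are being discarded. If they were not, the assay sentence is wrong.

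Magnitude is the whole of exploratory objective 5. A scale error would move the median as well as the mean, and could change response calls. The cap at 1280 acts only on the upper tail: it lowers the planned mean, standard deviation and maximum, leaves response rates alone, and reaches a median only when about half of a group is censored.

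**Working it through.** **Step 1: the plan's own figures.** Half the lowest dilution is 10/2 = 5, as stated. The two-fold series is 10 × 2^k. 1280 = 10 × 2^7 is the 8th level and 10,240 = 10 × 2^10 is the 11th. The two stated series therefore differ by three levels, a factor of 10,240/1280 = 8. The levels 2560, 5120 and 10,240 are missing from the fit.

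**Step 2: model for the scale question.** Let T be the titer as defined, c the control EGFP+ fraction and b the slope. The fraction infected at dilution d is

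EGFP(d) = c / (1 + (T/d)^b).

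At d = T this equals c/2, which is the definition. The documents give neither c nor b; both are assumed here, and the curves are noise-free.

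- Dilution where EGFP crosses an absolute 50%: T × (0.5/(c − 0.5))^(1/b) for c > 0.5. There is no crossing for c ≤ 0.5.
- Censoring under the text: all eight wells are below 50% when EGFP(1280) < 0.5, that is, when T > 1280 × (2c − 1)^(1/b).

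For b = 1 and T = 100 at c = 0.90, the crossing is 100 × 0.5/0.40 = 125 and the censoring threshold is 1280 × 0.80 = 1024. The fitted ID50 comes from a least-squares LL.2 fit to dilutions 10 to 1280. At T = 100 it lies above the crossing, because the fit tries to reach 100% when the data level off at c.

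| Control infection c | Absolute 50% crossing, T = 100, b = 1 | LL.2 fit, T = 100, b = 1 | LL.2 fit, T = 100, b = 2 | Censored above true T, b = 1 | Censored above true T, b = 2 |
|---|---|---|---|---|---|
| 100% | 100 | 100 | 100 | 1280 | 1280 |
| 95% | 111 | 116 | 109 | 1152 | 1214 |
| 90% | 125 | 136 | 121 | 1024 | 1145 |
| 80% | 167 | 200 | 162 | 768 | 991 |
| 70% | 250 | 322 | 240 | 512 | 810 |

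At c below 50%, EGFP(d) never exceeds c, so every curve satisfies the censoring rule. A serum with a true titer of 2, a non-responder, would be entered as 1280. At c = 50% exactly, the same holds for any serum with some neutralization. At c = 60% and b = 1, a true titer of 5 fits as 35, so a non-responder becomes a responder.

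**Step 3: after control-scaling.** Dividing by c makes the curve 1/(1 + (T/d)^b). The LL.2 fit then returns T exactly: inputs of 2, 40, 160 and 640 come back unchanged. An input of 3000 is also recovered by the fit, but the plan enters it as >1280.

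**Step 4: the cap alone, data normalised.** Any titer from 1280 to 10,240 is entered as 1280. As an illustration, assume lognormal titers with log10 SD 0.6, and values below 10 set to 5:

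| Assumed geometric mean titer | Share above 1280 | Mean, limit 1280 | Mean, limit 10,240 | SD, limit 1280 | SD, limit 10,240 |
|---|---|---|---|---|---|
| 80 | 2% | 181 | 206 | 263 | 453 |
| 320 | 16% | 495 | 785 | 443 | 1371 |

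The effect is modest when titers are low and large when they are high. The documents do not say which applies.

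**The case against.** The strongest reply is that the scale problem may be a gap in wording only. The definition in SAP 9.1 is explicitly relative to controls. A model with limits fixed at 0 and 100% makes most sense for control-scaled data, and negative controls are on every plate. The unscaled 50% appears only in the censoring sentence, and the SAP does not name the response variable of the fit. All of this stands, and it is why the scale point is conditional.

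It does not remove the need for a correction. The sentence on what the laboratory reports may have lost a word and may have meant percent reduction from control. The data would then be normalised, but the censoring rule would run backwards: a curve entirely below 50% reduction shows no half-neutralization, not a titer above 1280. The text needs correcting on either reading.

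The calibration standard might offset a scale shift. The SAP gives no rule for when or how it adjusts titers and does not describe it as scaling to the negative control, so its effect here is unknown.

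On range, the list in the fit may mean that the laboratory reports eight levels of a longer series. Capping at 1280 would then match the data analysed, and the substitution is openly declared. That is fair, but the SAP should say so and say why three levels go unused.

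Finally, the readout is exploratory, SAP 9.1.1 lists descriptive tables only, and medians and quartiles are already planned. This limits the consequence and sets the priority.

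**Conclusion.** The point holds as an internal inconsistency in SAP 9.1, with minor priority.

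- **Scale (conditional).** If wells are already divided by the plate's control, there is no bias and only wording is at fault. If not, the fitted ID50 is not the defined titer. For a true titer of 100 the inflation is 1.16 to 3.22-fold at slope 1 and 1.09 to 2.40-fold at slope 2, over assumed control infection of 95% down to 70%. Below 50% the rule fails altogether.
- **Range (unconditional as a text conflict).** Eleven levels are described and eight are fitted. Any numerical effect requires titers above 1280, which the documents neither report nor exclude.

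A reader might infer more than this, and the documents do not support it:

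- **That the titers are in fact biased, or biased in a known direction.** Control infection, slope and titer spread are not given. Without normalisation, the scale shift mostly raises titers in the middle of the range while the cap lowers high ones, so the net effect on a mean can go either way.
- **That different control infection in Part A and Part B would appear as a dose difference in the side-by-side boxplots.** The calibration adjustment intervenes, and its effect is unspecified.
- **That response calls could change only for titers close to 10.** This does not hold at lower control infection, as the results at 60% and below 50% show.

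**What to change.** 1. State in SAP 9.1 that each well is expressed as a percentage of its plate's virus-only (negative) control mean before the LL.2 fit, and apply the 50% and censoring rules on that scale. If the laboratory's values are already normalised in this way, say so and reword the censoring rule to match.
2. State one dilution range. If wells to 10,240 were read, fit them all and censor at >10,240. If only eight levels were run, correct the assay sentence.
3. Report the number of values above the limit by virus, visit and arm, next to the summary statistics already planned.

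**Cost.** SAP wording in every case. If the percentages are not normalised, existing wells must be refitted using control wells already on each plate. If wells at 2560 to 10,240 were read but not reported, the laboratory must transfer them. No new assays are needed.

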9.1.1 List of Tables

- Response rate table by lab, virus, visit number (visit month), and treatment arm (as applicable)
- Summary statistics for Ad Nab titers (min, 25th percentile, median, 75th percentile, max, mean, standard deviation) among all participants by lab, virus, visit number (visit month), and treatment arm (as applicable)
- Summary statistics for Ad Nab titers (min, 25th percentile, median, 75th percentile, max, mean, standard deviation) among participants with positive response by lab, virus, visit number (visit month), and treatment arm (as applicable)

9.1.2 List of Graphs

- Boxplots of Ad Nab antibody titers by virus, visit number (visit month), and treatment arm.

- Spaghetti plots of Ad Nab titers by virus, and treatment arm over time.
- (If applicable) Boxplots of Ad Nab titers by virus, visit month (Month 0 and Month 1), and treatment arm with Part A and Part B side-by-side.

9.2 Intracellular Cytokine Staining

Flow cytometry will be used to examine vaccine related HIV-1-specific CD4+ and CD8 responses using a validated ICS assay. A 17-color panel (experiment Assay ID 109; analysis plan 042) was used [8, 9]. The immunogenicity of this regimen will be assessed by intracellular cytokine staining (ICS) at CHIL for all available samples from participants from:

- Part A (n=11), visit 4 (1 month (M) post vaccination)
- Part B (n=20): visits 4 (M1, post first vaccination), 7 (M4, 1 month post the second vaccination) and 9 (M6.5, two weeks post the final vaccination)

Based on results from the above timepoints, others may be assessed, these include:

- Part A (n=11), visit 5 (M6)
- Part B (n=20): visit 10 (M12)

Several criteria will be used to determine if data from an assay are acceptable and can be statistically analyzed. The blood draw date must have been within the allowable visit window as determined by the protocol and assay results deemed unreliable for analysis by the lab will be excluded from the analysis. Post-infection samples from HIV-infected participants will be excluded. Participants with study administration error due to wrong dose administered will also be excluded. After sample thawing and overnight incubation, the viability of the PBMC must have been 66% or greater for testing to have proceeded. If it was not, a new specimen for that participant at that timepoint will be thawed for testing. If the PBMC viability of the second thawed aliquot is below this threshold, the ICS assay will be not performed, and no data will be reported to the statistical center for the participant and timepoint. For the negative control acceptance criteria, if the average cytokine response for the negative control wells is above 0.1% for either the CD4+ or CD8+ T cells, the sample will be retested. If the retested results are above 0.1%, the data will be excluded from analysis; otherwise, the retest data will be used.

The total numbers of CD4+ and CD8+ T cells must also have exceeded certain thresholds. If the number of CD8+ T cells is < 5,000 or CD4+ T cells is < 10,000 for any of the HIV-1 peptide pools or for one of the negative control replicates for a particular sample, data for that stimulation will be filtered. If both negative control replicates fail for number of T cells, the sample will be retested. If one negative control replicate fail for number of T cells, the negative control replicates with sufficient cells will be used. If both negative control replicates were included, then the sum of total cells and the sum of positive cells were used.

Peptide pools (Any Env) of CD4+ and CD8+ T cells will be calculated as the sum of ENV-1-PTEG-SEQ, ENV-2-PTEG-SEQ.

To assess positivity for a peptide pool within a T-cell subset, a two-by-two contingency table will be constructed comparing the HIV-1 peptide stimulated and negative control data. The four entries in each table are the number of cells positive for IFN- γ and/or IL-2 and the number of

cells negative for IFN- γ and/or IL-2 for both the stimulated and the negative control data. If both negative control replicates are included, then the average number of total cells and the average number of positive cells are used. A one-sided Fisher's exact test is applied to the table, testing whether the number of cytokine-producing cells for the stimulated data is equal to that for the negative control data. Since multiple individual tests (for each peptide pool) are conducted simultaneously, a multiplicity adjustment will be made to the individual peptide pool p-values using the Bonferroni-Holm adjustment method. If the adjusted p-value for a peptide pool is ≤ 0.00001 , the response to the peptide pool for the T-cell subset is considered positive. Because the sample sizes (i.e., total cell counts for the T-cell subset) are large, e.g., as high as 100,000 cells, the Fisher's exact test has high power to reject the null hypothesis for very small differences. Therefore, the adjusted p-value significance threshold is chosen stringently (≤ 0.00001). If at least one peptide pool for a specific HIV-1 protein is positive, then the overall response to the protein is considered positive. If any peptide pool is positive for a T-cell subset, then the overall response for that T-cell subset is considered positive.

IFN- γ and/or IL-2-expressing naïve and memory cells (Naïve (N), Central Memory (CM), Effector Memory (EM), and Terminally Differentiated (TEMRA)) will be analyzed in the final report as a percent of CD4 and CD8 T-cells, as well as a percent of IFN- γ and/or IL-2-expressing T-cells. All IFN- γ and/or IL-2-expressing naïve and memory T-cells belong to one of these four types.

